1. PROJECT TITLE

A single site evaluation of the inhibitory effects of topical ivermectin on serine protease activity and production of LL-37 cathelicidin peptide, biochemical markers of rosacea-specific inflammation and on the skin microbiome in rosacea (NCT02806414)

4. ESTIMATED DURATION OF THE STUDY

2 years

5. LAY LANGUAGE SUMMARY OR SYNOPSIS (no more than one paragraph)

This study will assess the role of topical Ivermectin 1% cream and its effect on protease and antimicrobial peptide expression and on the skin microbiome (the microorganisms that live on the skin) in rosacea. This is a single-site 16-week open-label study at University of California, San Diego. We will do this by first measuring serine protease activity and cathelicidin and skin microbiome of all subjects. All subjects will receive Ivermectin topical cream and will be instructed on how to apply it daily for 12 weeks. Participants will return for monthly visits during which their clinical symptoms of facial redness and number of facial papules will be scored, and they will have repeat tape stripping and/or skin swabs. At the end of the study, tape strips and skin swabs will be analyzed to determine serine protease activity and skin microbiome of participants at each of their visits and expression of cathelicidin (LL-37) mRNA. We will then look at changes in serine protease activity and LL-37 expression and skin microbiome over time, and we will also determine whether or not these changes correlate with disease severity.

6. SPECIFIC AIMS

1. To determine if 12 weeks of topical ivermectin to affected areas of facial skin can decrease biochemical markers of rosacea-specific inflammation and/or change the skin microbiome composition of rosacea patients
2. To validate and correlate the efficacy of topical ivermectin on rosacea and biochemical markers of rosacea.

7. BACKGROUND AND SIGNIFICANCE

Recent observations have shown that facial skin from patients with rosacea produce excess amounts of the serine protease kallikrein 5 (KLK5), and abnormal forms of the antimicrobial peptide cathelicidin (CAMP). In mice, abnormal CAMP and KLK5 expression influences inflammation, and administration of the forms of human CAMP found in rosacea results in inflammation, angiogenesis and vascular ectasia. In this study, we sought to further confirm the critical role of KLK5 and CAMP in rosacea by examining if the effects of a current human beneficial therapy correlated with changes in the expression of these genes. We measured KLK5 in cultured normal human epidermal keratinocytes (NHEKs), and found that differentiated keratinocytes in high calcium media (1.6 mM) greatly increased both KLK5 mRNA and protein compared to undifferentiated cells. Addition of Azelaic acid (AzA, 10-8 to 10-9 M) to differentiated NHEKs significantly decreased KLK5 in media (vehicle; 91.26 ± 22.58 ng/ml, 10-8 M AzA; 41.69 ± 15.08 ng/ml). Total protease activity was also significantly less in media recovered from keratinocytes treated with 10-8 M AzA. Furthermore, mice treated once a day for 9 d with topical application of AzA gel (15%, Finacea™) showed significantly less KLK5 and Camp mRNA compared with mouse skin treated with the vehicle alone (relative expression of KLK5 and camp was 55% and 32% of control, respectively). In conclusion, since an excess of KLK5 and cathelicidin has been hypothesized to contribute to the development of rosacea, finding that an effective treatment for rosacea can decrease expression of these molecules further supports the involvement of KLK5 and cathelicidin in the pathogenesis

of this disease.

Individuals with rosacea show high Cathelicidin antimicrobial peptide (CAMP) expression in lesional skin. High CAMP expression in rosacea is accompanied by an increase of its processing enzyme kallikrein 5 (KLK5), a major serine protease in skin epidermis. Combination of high CAMP and high protease activity by KLK5 increase makes CAMP in active form LL-37, which is not seen in normal skin. Persistent abundance of LL-37 induces inflammatory reactions in skin. Therefore, imbalance of CAMP and protease KLK5 is a key factor in rosacea pathogenesis.

Microbiome

Although the demodex mite has been described in the microbiome of rosacea, a specific driver of disease still remains to be found and the microbiome yet unidentified. In preliminary studies, our lab identified an increase in both the commensal organisms *Cutibacterium acnes* and *Staphylococcus epidermidis* after treatment with topical ivermectin. These findings correlated with a decrease in erythema and for *Staphylococcus epidermidis*, also a decrease in papule count. As different strains of these microorganisms have been associated with both a healthy microbiome and a diseased state of the microbiome, we hope to be able to expand on these early findings, and better identify the role of *Cutibacterium acnes* and *Staphylococcus epidermidis* in rosacea in hopes of establishing alternative treatments for patients with rosacea.

In this study, we will assess topical Ivermectin, which is FDA-approved in the treatment of rosacea, to enable us 1) to test if Ivermectin changes LL-37 mRNA and serine protease expression and skin microbiome composition in rosacea patients, and 2) to assess if improvement of rosacea symptoms is associated with a decrease in LL-37 and serine protease activity and related microbial changes.

8. PROGRESS REPORT

None

9. RESEARCH DESIGN AND METHODS

This trial is designed as a pilot study to determine the range and mechanism of monitoring biochemical surrogates of rosacea after daily topical Ivermectin 1% cream treatment. This is a single-site 16-week open label study at University of California, San Diego. Up to 25 subjects (age 18+) with at least one inflammatory papule (IGA>1) and at least mild erythema (see Clinical Assessment for Inclusion Criteria) will all be treated with topical ivermectin daily for up to 12 weeks with 4 in-office visits (screening, then monthly follow-ups for 3 months and one follow-up telephone visit one month after study medication completion). Twenty tape strip samples (similar to the tape strip method described in Dyjack, et. al. 2018) from each of the four sites will be obtained at each visit to determine KLK activity and LL-37 expression and/or up to twelve skin swabs to assess skin microbiome. Safety monitoring has been established based on both the most likely reactions and the most serious though extremely rare events. At each visit, in addition to one planned phone call, the subject will be queried tolerance of therapy and Adverse Events. The study will end with the last subject completing the telephone visit (Visit 5/week 16). If a patient does not return for a follow up visit after baseline, a replacement patient will be added.

The biochemical analysis of protease activity and LL-37 cathelicidin expression obtained by tape strip analysis at each time point and compared to baseline. Analysis of the tape strips will compare baseline to week 12 and also be correlated to the trends assessed in the tape strip analysis. The skin microbiome obtained by skin swab will also be analyzed at each time point and compared to baseline.

Ivermectin 1% cream is lawfully marketed in the U.S. as a topical treatment for inflammatory lesions of rosacea. Subjects will be instructed on the proper application of Ivermectin topical cream in accordance with the package insert, and they will apply a pea-sized amount for each area of the face that is affected daily. This research proposal therefore does not involve a route of administration, dose, or patient population that significantly affects the risk to benefit ratio associated with the use of the drug product.
Furthermore, this is a proof of concept study, and therefore, this investigation is not intended to support a

change in advertising of the drug, in labeling, nor in promoting the drug product.

Table of Events

Visit number	Screening /Baseline Visit 1*	2	3	4	5 (Phone Visit)
Time of Visit	Day -31 to Day 0	Week 4	Week 8	Week 12	Week 16
Demographic Information	x				
Inclusion/Exclusion criteria	x				
Informed consent	x				
Physical examination	x				
Rosacea Severity Score (IGA & CEA)	x	x	x	x	
Medical History	x				
Subject Satisfaction Assessment					
Tape strip	x	x	x	x	
Skin swabs	X	X	X	X	
Weigh/dispense study medication as needed	x	x	x	x	
Weigh and return study medication		x	x	x	
Adverse events	x	x	x	x	x

*Patients who require washout may be re-screened

VISIT 1 (Day 0)

Prior to beginning any study procedures, subjects will first be asked to review and sign the informed consent form. After obtaining informed consent, the inclusion/exclusion criteria will be reviewed. A brief medical history and physical exam will be performed in helping to assess whether the subject meets the required criteria for the study. Female subjects of child-bearing potential will complete a urine pregnancy test while in our office to ensure that they are not pregnant. Patients who meet the inclusion and exclusion criteria will then have their rosacea severity scored by two different standardized grading scales: IGA and erythema scale. At the screening visit may occur at the same time as your screening visit if none of your medications are excluded. Tape strips and/or skin swabs will be collected from 4 areas of involved rosacea facial skin. Subjects will then be given a pre-weighed tube of study medication and instructed to apply the medication daily. Subjects will also be instructed not to apply the study drug on the morning before the tape strip samples are collected on return visits. The total time for this visit will be approximately 1 hour.

VISIT 2 Week 4 (+/- 4 days)

On Visit 2, rosacea severity will again be evaluated. Tape strips and/or skin swabs will be collected from the same sites as in the initial collection. Patients will be instructed not to apply the study drug on the morning before the tape strip samples are collected on return visits. Study drug will be weighed, and additional drug will be provided as needed. The total time for this visit will be approximately 1 hour.

VISIT 3 Week 8 (+/- 4 days)

On Visit 3, rosacea severity will again be evaluated. Tape strips and/or skin swabs will be collected from the same sites as in the initial collection. Patients will be instructed not to apply the study drug on the morning before the tape strip samples are collected on return visits. Study drug will be weighed, and additional drug will be provided as needed. The total time for this visit will be approximately 1 hour.

VISIT 4 Week 12 (+/- 4 days)

On Visit 4, rosacea severity will again be evaluated. Tape strips and/or skin swabs will be collected from the same sites as in the initial collection. Patients will be instructed not to apply the study drug on the morning before the tape strip samples are collected on return visits. Study drug will be weighed, and additional drug will be provided as needed. The total time for this visit will be approximately 1 hour.

Visit 5 Week 16 (+/- 4 days) (phone follow-up)

Subjects will be contacted via phone to inquire about any adverse events experienced since the last in clinic visit. This phone call will take approximately 5 minutes.

Clinical assessments for inclusionary criteria:

IGA scale, a subjective 5-point measure of overall disease severity. IGA scores range from 0 to 4: 0 = no signs or symptoms present (clear); 1 = 1 to 2 small, noninflammatory papules (near clear); 2 = 3 to 10 papules/pustules (mild); 3 = 11 to 19 papules/ pustules (moderate); and 4 = 20 or more papules/pustules and nodules (severe).

Erythema scale: Scores range from 0-4: 0=none (no redness present); 1= mild (slight pinkness); 2= moderate (definite redness); 3=significant (marked erythema); and 4=severe (fiery redness). For inclusion criteria subjects will require at least mild erythema.

Lesional site identification and sample collection:

At Visit 1, Four ~20x20mm areas will be identified as clinically involved. These sites will be recorded to ensure subsequent sampling is from the same area during follow up visits (Visits 2-4).

Standard Tape stripping-Four sites will be selected, ideally two on the right cheek, and two on the left cheek. Commercially available stratum corneum sampling tape (such as D-Squame) will be used for 20 repeated tapings. To ensure consistent sampling methods, a pressure instrument (D500-D-squame® pressure instrument, CuDerm, Dallas, TX, USA) will be applied to the tape of the tape strip for uniform pressure. The tape is placed on the skin and removed and placed into an Eppendorf tube. This will be repeated 20 times. Tape stripping is a well-accepted less invasive method in dermatologic research that is now becoming an alternative to skin biopsy for certain assays. As we are doing here, we hope to validate this sampling method for use in larger studies and transition its use into clinical practice. In summary, 20 tape strips from each of the four sites, for a total of 80 tape strips will be collected at each visit for biochemical evaluation. They will be stored at -80°C until processing.

Standard Skin Swabs

Skin swabs will be done to collect bacteria from participants' skin. Swabs are then analyzed for the amount of bacteria and the presence of different bacterial species picked up by the swab. After swabbing, the swab are placed into either an empty Eppendorf tube (if analyzing the DNA of the bacteria present on the skin surface) or into a liquid medium such as tryptic soy broth (if analyzing the amount of bacteria present on the swabbed skin surface). These tubes are then stored at -80 degrees Celsius until analyzed for the data previously mentioned. The exact location of all swabbings, including whether the swabbing was taken from lesional or non-lesional skin in a patient with an inflammatory skin condition, will be recorded in the participant's file.

Laboratory Assessments

Processing of Tape-strips:

The tape strips from the same visit from the same patient will be combined and processed together. Tapes will be immersed in 1 ml of 10mM Tris-HCl (ph 7.8) + 0.1% TritonX and vortexed. Protein extracts will be completely lyophilized and the pellet dissolved in 40 μ l of PBS pH 7.4.

Cathelicidin LL-37 protein analysis (tape strips)

For quantification of cathelicidin, 2 μ l of each sample or serially diluted synthetic LL-37 peptide as a standard will be dotted onto a nitrocellulose membrane. The membrane will be blocked with 5% non-fat dry milk in PBS for 1 h, incubated overnight with rabbit antibody to LL-37 at 4°C followed by incubation for 1 h with HRP-conjugated goat antibody to rabbit IgG. The immunoreactions will be visualized by Western Lighting chemiluminescence reagent plus and the density of each blot measured with NIH Image and compared with standard controls. Alternatively, SELDI-TOF-MS (surface enhanced laser desorption ionization, time of flight, mass spectrometry) can be used to determine the cathelicidin peptide size. These procedures are developed in our laboratory to determine cathelicidin peptides from skin tape strip samples. Since the recovery of material from tape stripping may be variable, not all patients may have sufficient material for these studies.

Skin Swabs

Samples will be analysed for the bacterial composition of the skin either by amplicon sequencing utilizing 16s ribosomal RNA amplification, quantitative polymerase chain reaction (qPCR), whole genome shotgun metagenomics or other next generation sequencing method.

Statistical Methods

Demographics, Population, and Baseline Characteristics

Background and baseline demographic data and subject disposition data will be tabulated and presented for all enrolled participants. Subjects will be classified by severity of disease. The background and baseline characteristics will consist of age, race, sex, past and current medical conditions, and results from the physical examination. Continuous data (i.e., age) will be summarized descriptively by mean, standard deviation, median, and range. Categorical data (i.e., sex, race, and severity of disease) will be presented as enumerations and percentages. T-test will be used to evaluate continuous data and chi-squared test for categorical data.

Primary and Secondary Analysis

All information required will be entered into the Case Report Forms (CRFs). The objective of this trial is to determine if 12 weeks of topical ivermectin to affected areas of facial skin can decrease biochemical markers of rosacea-specific inflammation and affect the skin microbiome. Changes in lab measures before and after treatment will be compared pre and post Ivermectin treatment using paired sample t-tests. Variables with right-skewed distributions will be log transformed at each time (pre and post treatment) before analysis. If log transformations do not provide distributions suitable for 2-sample t-tests (based on violation to the normality assumption), the Wilcoxon Rank-Sum test will be employed.

Sample Size Calculation

Given this is a proof of concept study, no sample size calculation will be performed.

Safety Data

All AEs, including SAEs, occurring during the course of this study will be listed for all subjects. Adverse events resulting in discontinuation from the study will be listed separately. Other information collected about AEs (e.g., severity or relationship to study procedures) will be listed as appropriate.

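### The analysis text does not deliver Aim 2: its one correlation rule is self-referential, no clinical change is tested, and the papule number is not scheduled

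*Combined protocol and SAP*

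**What the plan says.** **The aim.** Section 6 gives Aim 2 as "To validate and correlate the efficacy of topical ivermectin on rosacea and biochemical markers of rosacea". The lay summary (Section 5) says of the marker and microbiome changes that "we will also determine whether or not these changes correlate with disease severity". The end of Section 7 gives the second purpose as "to assess if improvement of rosacea symptoms is associated with a decrease in LL-37 and serine protease activity and related microbial changes".

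**The analysis.** The overview of Section 9 holds the section's only correlation statement: the tape-strip analysis will compare baseline with week 12 and "also be correlated to the trends assessed in the tape strip analysis". The Primary and Secondary Analysis restates the objective as marker and microbiome change. It specifies paired t-tests on laboratory measures, with log transformation and a rank-based fallback. Elsewhere in the Statistical Methods, severity appears only as a way of classifying subjects at baseline.

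**The clinical measures.** The lay summary says that at the monthly visits "their clinical symptoms of facial redness and number of facial papules will be scored". The Table of Events has one severity row, IGA and CEA, at Visits 1 to 4, and the Visit 1 text names two scales, IGA and erythema. No row or visit description mentions a papule count. Lesion number enters through the IGA definitions: 1 to 2 papules for grade 1, 3 to 10 for grade 2, 11 to 19 for grade 3, and 20 or more with nodules for grade 4.

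**The concern.** Three sections promise a marker-severity result, and the text an analyst would work from does not say how to produce it. Followed literally, Section 9 yields paired comparisons of laboratory measures and a correlation of the tape-strip results with themselves. The clinical measure, the time interval and the coefficient for Aim 2 would then be chosen when the report is written, possibly with the results in view.

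The papule number raises a different risk. A missing analysis rule can be added later, but a count not written down at the visit cannot be rebuilt from an IGA grade. The count is also a natural measure for this study: Section 7 reports that in the preliminary work the rise in *Staphylococcus epidermidis* went with "also a decrease in papule count".

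**Working it through.** The plan gives no figure to reproduce: Section 9 states that no sample size calculation is performed. The check is a comparison of texts plus two small calculations.

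**1. Aim against analysis text**

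| Needed for Aim 2 | Where the plan supplies it |
|---|---|
| Intent to relate markers to severity | Sections 5, 6 and 7 |
| Clinical data over time | Table of Events: IGA and CEA (read here as the erythema scale), Visits 1 to 4 |
| Test of clinical change | Not given |
| Clinical variable in the correlation | Not given; Section 9 names tape-strip trends on both sides |
| Coefficient or model, interval, time span | Not given |

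Reading the Section 9 sentence as a slip for clinical trends supplies the intended partner. The Primary and Secondary Analysis would still have no clinical measure and no method.

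**2. What the IGA bands keep of a papule count**

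The inputs are the grade definitions under the clinical assessments in Section 9.

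- 10 to 3 papules: a fall of 7/10 = 70%; grade 2 before and after.
- 19 to 11 papules: a fall of 8/19 = 42%; grade 3 before and after.
- 11 to 10 papules: a fall of 1/11 = 9%; grade 3 becomes grade 2.

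The first two are the widest falls that can stay within bands 2 and 3. They show what the scale can hide, not how often it will: the documents give no distribution of counts.

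**3. Precision of the proposed correlation**

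Inputs: at most 25 subjects (Sections 9 and 10). Fewer pairs are likely, because sampling is tape strips and/or swabs and Section 9 warns that some patients may not yield enough material. The value of 15 pairs and the observed correlation r = 0.4 are assumptions.

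The interval for a Spearman correlation is tanh(atanh(r) ± 1.96 × sqrt((1 + r²/2)/(n − 3))), with atanh(0.4) = 0.424 and 1 + r²/2 = 1.08.

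- n = 25: sqrt(1.08/22) = 0.2216; 0.424 ± 0.434; interval -0.01 to 0.70.
- n = 15: sqrt(1.08/12) = 0.300; 0.424 ± 0.588; interval -0.16 to 0.77.

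The formula must be written out in the plan. The plain Fisher form, with standard error 1/sqrt(n − 3), gives 0.006 to 0.687 at n = 25 and so falls on the other side of zero. In simulations with n = 25 and 15, including clinical change rounded to five levels, the Spearman interval covered at about 95 to 96%, so tied grades are not an obstacle.

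**The case against.** The strongest reply is that nothing is lost. The commitment appears in three sections, IGA and erythema are collected at every clinic visit, and any statistician would see that the Section 9 sentence meant clinical trends. This stands in part. A reader might infer that the study cannot answer Aim 2, or will end without a marker-severity result; the documents do not support that, because both the intent and the clinical grades are there. What is missing is the operative rule.

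On papules, the statement sits in a lay summary and uses the verb for scoring, so it may paraphrase the erythema scale and IGA. The papule count in Section 7 belongs to earlier work. The case report form is not in the documents and may already hold a count. A reader might conclude that counts will not be recorded; that cannot be shown. Rewording the lay summary would also remove the mismatch, but it would not keep the information within the bands.

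A reader might also wish to count marker-by-scale pairs as a measure of multiplicity. The plan gives no closed list of markers, so any such count would be constructed. Whether LL-37 means mRNA or protein, and which microbiome assay is used, are separate marker-definition questions that affect Aim 1 equally.

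Finally, this is a pilot and proof-of-concept study. That is a good reason to call the correlations exploratory and to omit a power calculation. It is not a reason to leave one of two aims without a stated analysis.

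**Conclusion.** The point holds in a limited form and should be acted on. As written, Section 9 does not deliver Aim 2: its single correlation rule names no clinical variable, and the Primary and Secondary Analysis covers laboratory measures only. This rests on the text alone and is firm. That the sentence is a slip is an inference, though a likely one.

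The papule strand is conditional. If the case report form has no count, falls of up to 70% within grade 2 and up to 42% within grade 3 leave no trace in the IGA. If it has one, only the schedule and visit text are out of step.

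The wide correlation intervals are not a further defect. They are the reason to report intervals and to label the results exploratory. The paired comparisons for Aim 1 are not affected.

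**What to change.** 1. **Section 9, overview.** In the sentence that contains "also be correlated to the trends assessed in the tape strip analysis", replace the tape-strip trends with: *change in IGA, erythema grade and papule/pustule count*.
2. **Table of Events and visit text.** Record the raw papule/pustule count at Visits 1 to 4. If the case report form already holds it, only the schedule and text change.
3. **Primary and Secondary Analysis.** Add: *Change from baseline to week 12 in IGA, erythema grade and papule/pustule count will each be tested by Wilcoxon signed-rank test. Baseline-to-week-12 change in each marker will be related to each clinical change by Spearman correlation, reported with the number of paired subjects and a 95% interval, tanh(atanh(r) ± 1.96 × sqrt((1 + r²/2)/(n − 3))).*
4. **Status of the correlations.** Either label all of them exploratory, or name one lead pair before any assay result is seen. The lay summary makes the second option feasible: "At the end of the study, tape strips and skin swabs will be analyzed to determine serine protease activity". This assumes that samples are in fact held until then; the documents do not show how far the study has progressed.

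The cost is one corrected sentence, one short paragraph, at most one form field, and a little time at four existing visits where IGA already requires a judgement of lesion number. No visits, samples or patients are added. The downside is that the intervals will be wide, and wider still where fewer than 25 subjects have both a marker and a clinical change.

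### LL-37 mRNA and serine protease activity are named as readouts but have no written assay, and the LL-37 peptide reading has no measure of recovered material, so a systematic yield shift could mimic or hide a change

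*Combined protocol and SAP*

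**What the plan says.** **What is to be measured.** The documents differ.

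- Section 1 (title): effects "on serine protease activity and production of LL-37 cathelicidin peptide".
- Section 5 (synopsis): "expression of cathelicidin (LL-37) mRNA".
- Section 7, last paragraph, first objective: "to test if Ivermectin changes LL-37 mRNA and serine protease expression".
- Section 9, opening paragraph: the strips "will be obtained at each visit to determine KLK activity and LL-37 expression".

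**How the strips are handled (Section 9).** Twenty strips from each of four recorded sites give 80 per visit. Under Processing of Tape-strips, "The tape strips from the same visit from the same patient will be combined and processed together" in a Tris/Triton buffer, and "Protein extracts will be completely lyophilized and the pellet dissolved" in 40 microlitres. For LL-37, 2 microlitres of each sample are blotted and compared with a synthetic LL-37 standard; a mass spectrometry method for peptide size is the alternative. The same section warns that recovery may vary and that some patients may not yield enough material. Collection is standardised: "To ensure consistent sampling methods, a pressure instrument" is applied.

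**Analysis and design.** Pre- and post-treatment laboratory values are compared by paired t-tests, on the log scale if right-skewed. There is one open-label arm of up to 25 subjects and no sample size calculation. The plan also says of tape stripping that "we hope to validate this sampling method for use in larger studies".

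**The concern.** There are three linked gaps between what the study sets out to measure and what the laboratory section can deliver.

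- **mRNA.** If every strip of a visit goes into one protein extract, nothing remains for RNA. A readout named in two places would go unmeasured, and the loss could not be repaired once the strips had been processed.
- **Protease activity.** It is in the title, the synopsis and the stated purpose of the strips, but no substrate, readout or unit is given.
- **Yield.** A fixed volume read against a peptide standard gives LL-37 per volume of extract, which rises and falls with the amount of skin material recovered. Pairing removes stable differences between patients but not a shift between visits. With no concurrent control, a change in yield from baseline to week 12 cannot be told apart from a drug effect. This also matters for the hope of validating the sampling method, which needs yield by visit.

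**Working it through.** **Step 1: trace each named readout to an assay in Section 9.**

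| Readout | Named in | Assay described for strips |
|---|---|---|
| LL-37 peptide | Title | Yes: antibody dot blot, or mass spectrometry |
| LL-37 mRNA | Sections 5 and 7 | None: no RNA preservation, extraction or amplification |
| Serine protease / KLK activity | Title, Sections 5 and 9 | None |
| Recovered material (total protein) | Not named; variable recovery acknowledged in Section 9 | None, and no sufficiency threshold |

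The qPCR and sequencing in Section 9 are for bacteria on the swabs. The strip method is modelled on a cited study of tape strip RNA sequencing (Section 22), so an RNA step may have been intended, but none is written. Strips per visit: 4 × 20 = 80, all pooled. Fraction of extract read for LL-37: 2/40 = 5%.

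**Step 2: what a yield shift does to the paired test.** The plan states no power, SD or effect size, so there is no figure of its own to reproduce. On the log scale,

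measured log change = true log change per unit protein + log(yield ratio, week 12 / baseline).

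Random variation in yield averages zero and only widens the SD. In a simulation of purely random yield variation at n=25, the two-sided error rate stayed at 5.0%. A systematic shift moves the mean.

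*Assumptions (none are in the documents):* two-sided 5% test; SD of paired log change 0.4, 0.8 or 1.0; n=25 (the plan's maximum) or n=15 (enrolment is only capped, strips are and/or swabs, and some samples may be insufficient).

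The probability of a significant decrease is P(T ≤ −t), with T non-central t on n−1 degrees of freedom, non-centrality √n × shift / SD, and t = 2.064 (n=25) or 2.145 (n=15). With no shift it is 2.5%.

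Example: a 20% lower yield gives ln(0.8) = −0.223. At n=25 and SD 0.4 the non-centrality is 5 × (−0.223)/0.4 = −2.79, and the probability is 76.3%.

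**False significant decrease, no true change per unit protein**

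| Yield shift | n | SD 0.4 | SD 0.8 | SD 1.0 |
|---|---|---|---|---|
| 20% lower | 25 | 76.3% | 26.7% | 18.7% |
| 20% lower | 15 | 52.1% | 17.0% | 12.4% |
| 10% lower | 25 | 24.3% | 9.2% | 7.3% |
| 10% lower | 15 | 15.7% | 6.9% | 5.7% |
| 5% lower | 25 | 8.9% | 4.9% | 4.3% |
| 5% lower | 15 | 6.7% | 4.2% | 3.8% |

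Simulation with 200,000 trials per setting agrees for the 20% shift at SD 0.4 and 0.8: 76.4% and 26.9% (n=25), 52.1% and 17.1% (n=15).

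**Step 3: the opposite direction.** Take a true 30% fall per unit protein, ln(0.7) = −0.357. A 20% higher yield adds ln(1.2) = 0.182, leaving −0.174, an apparent fall of 16% (0.7 × 1.2 = 0.84).

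| n | SD | Power, no yield shift | Power, yield 20% higher |
|---|---|---|---|
| 25 | 0.4 | 99.0% | 55.2% |
| 25 | 0.8 | 57.1% | 18.1% |
| 15 | 0.4 | 89.4% | 34.9% |
| 15 | 0.8 | 36.3% | 12.1% |

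**The case against.** **The denominator is a choice.** Four recorded sites of fixed size, a fixed strip count, uniform pressure and a peptide standard give LL-37 per sampled area, which is a legitimate quantity. Calling a change false because LL-37 per unit protein did not move assumes the other denominator, and that one would itself move if treatment altered total protein. This stands: neither denominator can be declared correct. It argues for reporting both and does not remove the need to measure yield.

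**The size is assumed.** No passage gives a yield, an SD or a direction. The largest figure needs a 20% systematic shift, a small SD and all 25 subjects; a 5% shift gives 4.9% to 8.9% at n=25 (SD 0.8 to 0.4). This stands too. The percentages show sensitivity, not likelihood.

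**The mRNA point may be loose wording.** It is absent from the title, from the Specific Aims and from the statistical objective, and there is no formal outcome list. If the peptide was meant, two edits settle it. But the documents do not say which was meant, and pooling closes off the alternative.

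**The protease gap is missing detail.** The same extract may be usable for an activity assay. On its own this would be a request for clarification.

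**It is a pilot.** It is a proof of concept, not intended to support labelling or advertising changes. That lowers the stakes, but the pilot's stated purpose is to learn how to monitor these markers, and recovery by visit is part of that.

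**Conclusion.** The concern holds and should be fixed. Two parts rest on the text alone: LL-37 mRNA is named in two sections with no route to measure it once all 80 strips are pooled, and protease activity has no described assay. The third part is a demonstrated possibility, not a demonstrated bias. LL-37 is read without any measure of recovered material, so a systematic yield shift in either direction would pass unseen in a single-arm comparison.

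Under the assumed SDs of 0.8 to 0.4, a 20% lower week-12 yield raises the chance of a significant decrease from 2.5% to 27%–76% at n=25 and 17%–52% at n=15. A 20% higher yield cuts power for a true 30% fall from 57%–99% to 18%–55% at n=25, and from 36%–89% to 12%–35% at n=15. These figures take LL-37 per unit protein as the target and depend on yield shifts that the documents neither support nor exclude. Safety is not affected.

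**What to change.** 1. **Settle the outcome.** Replace LL-37 mRNA with LL-37 peptide in the synopsis and Section 7. If mRNA is wanted, set aside the strips of one site before pooling and describe the RNA assay.
2. **Measure yield.** Determine total protein in each 40 microlitre extract and report it by visit. Analyse log(LL-37 / total protein) and log(protease activity / total protein) alongside the per-sampled-area readings. State in advance that if the two readings disagree, the result is reported as yield-dependent. Define disagreement before processing, for example as estimates of opposite sign, or only one 95% interval for the log change excluding zero.
3. **Describe the protease assay** to be run on the same extract, in Laboratory Assessments.
4. **Report the number of insufficient-material samples by visit**, with the criterion used.

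**Cost.** Wording, a routine protein assay and a few microlitres of each extract. The protein and protease assays draw on a small volume that the plan already expects to be short for some patients, so the order of assays should be stated. The RNA option costs more: 20 of 80 strips per visit (25%) would be lost to the protein assays. The changes need to be made before the strips are pooled.
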